- ^k A full physical examination will be performed at Screening, at check-in for the study, and at the End of the study/Early Termination Visit. A physical examination should also be performed on any participants with ongoing adverse events prior to discharge from the unit. Otherwise, a symptom-driven physical examination may be performed at other times, at the Principal Investigator's discretion.
- ^l Height at screening only.
- ^m While in the CRU, study intervention will be administered after an overnight fast (ie, at least 10 hours) at the same time every morning; drug is to be administered with 240 mL of water and meals should be delayed a minimum of 2 hours after dosing. As an outpatient, participants are expected to take ALXN1840 at approximately the same time daily (+/-1 hour). Participants should take the medication with a glass of water on an empty stomach; meals should be delayed a minimum of 2 hours after dosing.
- ⁿ During the outpatient period, participants will use SMS text messaging to confirm study intervention administration.
- ^o Blood sampling for PK/PD will occur before ALXN1840 administration and represents a predose trough. See [Table 2](#) for PK/PD sampling on Days 1, 25, 29, and 39.
- ^p PK/PD collection will include timepoints described in the schedule of PK/PD assessment for Days 1, 25, 29, and 39 ([Table 2](#)).
- ^q Samples for serum chemistry will be obtained following a fast of at least 8 hours at the Screening Visit and at check-in. In case of rechecks, and postdose serum chemistry, participants may not have fasted for 6 or 8 hours before the serum chemistry sample is taken.
- ^r Laboratory assessment including chemistry, hematology, and coagulation parameters should be performed on Days -8, -1, 8, 23, and 28 only.
- ^s Menstruation check is for women only; women of childbearing potential should only be enrolled after a negative serum pregnancy test result at Screening. Additional urine pregnancy testing will be standard for the protocol unless serum testing is required by site policies, local regulation, or Institutional Review Boards (IRBs)/Independent Ethics Committees (IECs) (Section 10.2). In addition to pregnancy tests detailed at the visits in the SoA, females of childbearing potential will be required to perform urine pregnancy tests at least every 4 weeks at their home or the study site throughout their time in the study.

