Following ALXN1840 administration, the active drug moiety tetrathiomolybdate rapidly binds copper to form TPC, mostly in the liver and blood, and presents as such in the systemic circulation. If TPC is not rapidly formed, tetrathiomolybdate spontaneously undergoes serial hydrolysis to form molybdate, the most common form of nutrient molybdenum, and is excreted in the urine. Total molybdenum concentration has been measured as a surrogate of ALXN1840 PK; however, total molybdenum concentration cannot distinguish whether the molybdenum is protein bound (mostly as TPC), free active drug as ALXN1840, intermediate hydrolysis products, or molybdate. To better characterize the amount of non-TPC-bound drug and its unbound degradation products, plasma PUF-molybdenum has also been measured, which

represents the free parent drug (ALXN1840), short-lived intermediate hydrolysis products, and molybdate, which may have originated from the tetrathiomolybdate or from food intake as a micronutrient. Total molybdenum PK and free molybdenum PK serve as surrogate measures of ALXN1840 PK. To better characterize the ADME of ALXN1840, the PK of both total molybdenum and PUF-molybdenum will be characterized and described.

This study is designed to provide an extensive assessment of copper and molybdenum balance over the first 40 days of treatment with ALXN1840 and support a more robust understanding of the effects of duration of treatment and dose of ALXN1840 on copper balance. Half-life estimates for total molybdenum in Study WTX101-201 were reported to be approximately 24 hours at steady state on Days 84 and 168, while in healthy participants, total molybdenum half-life was measured closer to 51 hours. With a half-life within this range, the sample collection periods include assessment of copper and molybdenum balance both during accumulation and at steady state for both the 15 mg/day and 30 mg/day doses. The study will include both intake and output collection as well as PK and copper assessments (ie, ceruloplasmin-bound copper and labile bound copper [LBC]) to inform the relationship between balance measurements and copper and molybdenum levels in the blood.

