Finally, preclinical data from ALXN1840 ADME study suggest the potential for molybdenum accumulation in the liver of participants with WD; therefore, an assessment of molybdenum balance will help determine whether steady state has been reached as defined by a molybdenum balance of neutral during the collection period. Because molybdenum is a necessary micronutrient and serves as a cofactor for a number of enzymes and may exist in intracellular stores, small variations in molybdenum balance could be due to molybdate rather than ALXN1840.

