7.2.2. Secondary Analyses

Secondary analyses will be performed using the FA Set. The secondary endpoints include:

- Change from pre-dose baseline in mean daily copper balance during ALXN1840 accumulation and steady-state periods for each dose
- Mean daily copper quantified in food, drink, feces, and urine, and mean plasma total copper, and mean LBC, during ALXN1840 accumulation and steady-state periods for each dose
- Mean daily molybdenum quantified in food, drink, feces, and urine, and mean plasma total molybdenum, during ALXN1840 steady-state period for each dose

- Mean daily molybdenum balance as demonstrated through measurement of molybdenum intake (in food, drink and ALXN1840), and molybdenum output (feces and urine), during ALXN1840 steady-state period for each dose
- Accumulation of molybdenum as determined by molybdenum balance
- PK parameters for plasma total and PUF-molybdenum

The secondary continuous endpoints will be analyzed using the same methods described for the primary analysis. Molybdenum balance will include the additional molybdenum intake from ALXN1840. The nominal amount of molybdenum contained in ALXN1840 will be used and is estimated as 3.33 mg in each 15 mg tablet per the following calculation: $95.96 \text{ g/mol (molecular weight of molybdenum)} / 432.54 \text{ g/mol (molecular weight of bis-choline tetrathiomolybdate)} * 15 \text{ mg/tablet} = 3.33 \text{ mg molybdenum}$. The periods of interest described in Section 7.2.1 will be utilized as appropriate. The daily molybdenum balance for each subject will be plotted as will the mean daily molybdenum balance.

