For ALXN1840, equivalent molybdenum dose will be used to calculate total molybdenum CL/F and V_d/F values as described in Section 7.2.2. For ALXN1840 30 mg equivalent molybdenum dose is 6.66 mg.

Additional plasma PK parameters may be calculated if deemed appropriate.

For the PK analysis, values below the limit of quantification (BLQ) prior to the first measurable concentration will be set to zero whereas the rest of all other BLQ values will be treated as missing.

Pharmacokinetic parameters derived from plasma concentrations of total molybdenum and PUF molybdenum will be presented in data listings and summarized by analyte, treatment (dose), and day using the following descriptive statistics: number of participants, arithmetic mean, SD, arithmetic CV, GM, GMCV, 95% CI, median, minimum, and maximum. Geometric mean and geometric CV will be presented for C_{\max} and AUCs only. When calculating the geometric mean, values of 0 will be discarded.

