7.4.5. Pharmacokinetic Statistical Analyses

Attainment of steady state will be evaluated using stepwise testing for linear trend.

Plasma total molybdenum and total copper AUC_{tau} relationship will be assessed using linear least squares regression and E_{max} model.

If data permit, dose-proportionality for ALXN1840 will be assessed graphically and by using a power model (Smith, 2000; Newlands, 2006; EMA, 2010). The following PK parameters obtained on Days 25 and 39 will be assessed for dose proportionality: C_{max_n} and AUC_{t_n}. The log (PK parameters for plasma total and PUF molybdenum) will be included as a response variable and log (dose) will be included as a fixed effect in the power model:

$$\log(\text{PK Parameter}) = \mu + \beta * \log(\text{Dose}),$$

where $\beta = 1$ indicates perfect dose proportionality. Estimation of β , along with its 90% CI, will be provided.

Additional approaches to test dose proportionality, such as an ANOVA model, will be explored (Calvo, 2005).

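### Plasma molybdenum PK is not corrected for pre-dose (dietary) molybdenum, so CL/F is biased low if the pre-dose level is quantifiable; the size is not known from the documents

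*SAP*

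**What the plan says.** **Dose.** SAP 7.2.2 sets the molybdenum content of a tablet, which "is estimated as 3.33 mg in each 15 mg tablet per the following calculation". SAP 7.4.3 carries this into clearance: the "equivalent molybdenum dose will be used to calculate total molybdenum CL/F" (and Vd/F), and "For ALXN1840 30 mg equivalent molybdenum dose is 6.66 mg". Only drug molybdenum is counted.

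**Analyte.** Protocol 4.2 says that a total molybdenum assay cannot separate bound drug, free drug, hydrolysis products and molybdate. It describes the ultrafiltrate (PUF) fraction as including "molybdate, which may have originated from the tetrathiomolybdate or from food intake as a micronutrient". On molybdenum balance, the same section allows for small variations unrelated to drug: "Because molybdenum is a necessary micronutrient and serves as a cofactor for a number of enzymes and may exist in intracellular stores".

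**Correction.** Protocol 9.4.4 and SAP 7.4.3 calculate noncompartmental parameters from the measured concentrations. The only subtraction is the carry-over adjustment of the Day 29 profile, used for the 30 mg accumulation ratio. Change from Baseline is specified for the copper PD measures and biomarkers (SAP 7.4.2), not for molybdenum. In the PK analysis, values below quantification (BLQ) before the first measurable concentration are set to zero.

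**Dose proportionality.** SAP 7.4.5: "If data permit, dose-proportionality for ALXN1840 will be assessed graphically and by using a power model". The parameters named are the dose-normalised Cmax and AUCt on Days 25 and 39, and proportionality is read as a slope of 1.

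**Available data.** Protocol Table 2 schedules a sample 0.5 h before the Day 1 dose, and a footnote to Table 1 says "Blood sampling for PK/PD will occur before ALXN1840 administration and represents a predose trough". SAP 7.1.3.2 already tabulates baseline total and PUF molybdenum.

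**The concern.** CL/F divides a drug-only dose by an AUC that may hold drug plus food molybdenum. Any quantifiable background inflates the denominator and lowers CL/F. A background that stays constant does not double when the dose doubles, so it also makes exposure look less than proportional to dose. It enters the accumulation ratios as well.

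The SAP is not consistent on this. Its molybdenum balance counts food, drink and tablet as separate inputs, while its PK section credits all plasma molybdenum to the tablet.

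At stake are a secondary objective (steady-state molybdenum PK) and an exploratory one (dose proportionality). The accumulation ratios also matter, because Protocol 2.2 and 4.2 raise possible tissue accumulation of molybdenum.

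**Working it through.** **The plan's own figure.** 95.96 / 432.54 × 15 = 3.328 mg, and × 30 = 6.656 mg. These agree with the SAP's 3.33 and 6.66 mg.

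**Assumptions.** Let A be the drug-derived AUCtau at 15 mg and b the background over 24 h (24 × pre-dose concentration), with r = b/A. The documents do not give b, so r is assumed at 0.01, 0.05, 0.10 and 0.20. Drug exposure is taken as truly proportional, Days 25 and 39 as steady state, and the background as constant.

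**CL/F and slope.** Observed AUCtau is A(1 + r) at 15 mg and A(2 + r) at 30 mg.

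- Apparent/true CL/F is 1/(1 + r) at 15 mg and 1/(1 + r/2) at 30 mg.
- The slope on un-normalised AUC is log2[(2 + r)/(1 + r)], against a true value of 1.
- The slope on dose-normalised AUC is that value minus 1, against a true value of 0. The shift is the same.

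| r | CL/F low, 15 mg | CL/F low, 30 mg | Slope, un-normalised | Shift |
|---|---|---|---|---|
| 0.01 | 1.0% | 0.5% | 0.993 | −0.007 |
| 0.05 | 4.8% | 2.4% | 0.965 | −0.035 |
| 0.10 | 9.1% | 4.8% | 0.933 | −0.067 |
| 0.20 | 16.7% | 9.1% | 0.874 | −0.126 |

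For Cmax, r is background over drug Cmax. That is smaller than the AUC-based r, because Cmax exceeds the average concentration.

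**15 mg accumulation ratio (AUC).** With rapid absorption the true ratio is 1/(1 − 2^(−24/t½)). The 2-day half-life in the note to the objectives (Protocol 3) gives 3.4. The 24 h steady-state estimate (Protocol 2.2) gives 2.0. The observed ratio is (1 + r)/(1/true + r). At r = 0.10:

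- true 3.4: 1.10 / (0.294 + 0.10) = 2.79
- true 2.0: 1.10 / (0.50 + 0.10) = 1.83

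**30 mg accumulation ratio (AUC).** The extrapolated Day 28 profile contains background, so subtracting it from Day 29 removes background from the denominator. The Day 39 numerator keeps it. Take a 48 h half-life, true ratio 3.41 and r = 0.10, in units of A. The numerator is 2 + 0.10 = 2.10, and the drug part of the denominator is 2/3.414 = 0.586.

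- Background carried forward in full: 2.10 / 0.586 = 3.58.
- Background extrapolated as if it decayed with the drug: the share removed is (1 − 0.707)/0.347 = 0.845, leaving 0.155 × 0.10 = 0.0155 in the denominator. The ratio is 2.10 / 0.601 = 3.49.

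Either way the ratio moves up slightly.

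**Day 1 illustration.** This uses one compartment, an assumed absorption rate of 0.8/h, Table 2 sampling times, and CL/F from AUC to infinity. At r = 0.05, CL/F is about 16% low for a 24 h half-life and 27% low for 51 h. Half-life reads as 26.8 h instead of 24.1 h, and 61.0 h instead of 51.3 h. The figures depend on the assumed model; they show only that extrapolated parameters can be more sensitive than steady-state ones.

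**After correction.** Subtracting b returns CL/F to its true value at both doses, and the slope to 1 (un-normalised) or 0 (dose-normalised).

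**The case against.** The strongest case is that this may not matter. No pre-dose plasma concentration is given. At r = 0.01 the effect is about 1% on CL/F, and with BLQ pre-dose values the corrected and uncorrected parameters coincide. The primary endpoint is copper balance, there are about 10 participants and no hypothesis tests, and dose proportionality is exploratory. Concentrations are listed, baseline molybdenum is summarised and SAP 7.4.3 allows extra parameters, so a correction could be made later from the same data. All of this stands. It limits the importance of the point, but it leaves the direction of the CL/F bias unchanged and does not make the correction prespecified.

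The remedy also rests on a stable background. Day 1 pre-dose is a single fasted sample after seven days of controlled diet. Day 25 follows an outpatient period with no stated molybdenum control, and the minimum diet equilibration is 48 hours. This stands too, and is why the uncorrected values should stay. In favour of the sample, tetrathiomolybdate within the previous year is an exclusion, and participants agree to avoid molybdenum-containing minerals.

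A reader might infer more than the documents support:

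- **That bias is certain.** It depends on a pre-dose level that neither document reports.
- **That the fitted slope falls below 1 because of background.** The SAP names dose-normalised parameters, for which proportionality is a slope of 0. As written, background moves the slope below 0. The mismatch with a reference value of 1 is a separate and larger error.
- **That all accumulation ratios are understated.** This holds at 15 mg. The Day 29 subtraction reverses the direction at 30 mg.
- **That PUF molybdenum is affected more than total.** The wording on food origin concerns PUF, but Protocol 4.2 also says that the drug hydrolyses to molybdate and so feeds the same pool. No exposure figures are given to compare.

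**Conclusion.** The concern holds in conditional form. The plan sets a drug-only dose against concentrations that can include food molybdenum, and no step removes the pre-dose level. If that level is quantifiable, steady-state CL/F is low by r/(1 + r) at 15 mg and by about half as much at 30 mg, the 15 mg accumulation ratio is understated, the 30 mg ratio is slightly overstated, and the power-model slope moves down. The sizes above rest on assumed values of r, a constant background, steady state on Days 25 and 39, and simple one-compartment accumulation. The bias is in secondary and exploratory PK outputs and does not touch the primary endpoint. It merits a change because the sample needed is already scheduled and the cost is small.

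**What to change.** In SAP 7.4.3 and 7.4.5, prespecify baseline-corrected total and PUF molybdenum parameters:

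- Subtract the participant's Day 1 pre-dose value from each concentration, set negative results to zero, and treat a BLQ pre-dose value as zero.
- Apply this to Cmax, AUC, CL/F, Vd/F, half-life, the accumulation ratios and the power model, and report the results next to the uncorrected values.
- For the 30 mg accumulation ratio, correct the Day 28, Day 29 and Day 39 profiles before the carry-over subtraction, so that background is not removed twice.
- First resolve the power-model mismatch by fitting un-normalised Cmax and AUC against a slope of 1.

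The cost is SAP wording and a second set of parameters, with no new samples. The downsides are that one pre-dose value adds some noise, flooring at zero can bias slightly upward, and subtraction assumes that the background is stable and unaffected by dosing. Showing both sets lets readers judge.

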7.4.4. Pharmacodynamic Parameter Analyses

The following plasma PD parameters, as data permit, will be calculated for plasma total copper, PUF copper, and LBC on Days 1, 25, 29, and 39 using noncompartmental methods with Phoenix[®] WinNonlin[®] (Certara USA Inc., Princeton, New Jersey) Version 8.0 or higher, or SAS Version 9.4 or higher (SAS Institute Inc., Cary, North Carolina), as applicable. Calculations will be based on the individual actual sampling times relative to the actual reference ALXN1840 dosing times recorded during the study.

- Maximum observed effect after dosing (CE_{\max})
- Time after dosing at which the maximum effect was observed (TE_{\max})
- Time after dosing at which the last quantifiable concentration was observed (TE_{last})
- Trough (pre-dose) effect concentration observed at the start of the dosing interval (CE_{trough})
- Area under the effect versus time curve (AUEC) from the start of dose administration to the last observed quantifiable concentration ($AUEC_t$)
- AUEC over the dosing interval ($AUEC_{\tau}$)

Additional plasma PD parameters may be calculated if deemed appropriate.

For the PD measures plasma total copper, LBC, and dNCC parameter calculations, concentrations BLQ prior to the first measurable concentration will be set to zero; all other BLQ

values will be treated as missing. For PUF copper parameter calculations, all BLQ values will be set to zero.

Pharmacodynamic parameters derived from plasma concentrations of total copper, PUF copper, dNCC, and LBC will be presented in data listings and summarized by analyte, treatment (dose), and day the following descriptive statistics: number of participants, arithmetic mean, SD, arithmetic CV, GM, GMCV, median, minimum, and maximum.

7.4.5. Pharmacokinetic Statistical Analyses

Attainment of steady state will be evaluated using stepwise testing for linear trend.

Plasma total molybdenum and total copper AUC_{tau} relationship will be assessed using linear least squares regression and E_{max} model.

If data permit, dose-proportionality for ALXN1840 will be assessed graphically and by using a power model (Smith, 2000; Newlands, 2006; EMA, 2010). The following PK parameters obtained on Days 25 and 39 will be assessed for dose proportionality: C_{max_n} and AUC_{t_n}. The log (PK parameters for plasma total and PUF molybdenum) will be included as a response variable and log (dose) will be included as a fixed effect in the power model:

$$\log(\text{PK Parameter}) = \mu + \beta * \log(\text{Dose}),$$

where $\beta = 1$ indicates perfect dose proportionality. Estimation of β , along with its 90% CI, will be provided.

Additional approaches to test dose proportionality, such as an ANOVA model, will be explored (Calvo, 2005).

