5.1.3. Exploratory Objectives and Endpoints

The exploratory objectives and endpoints are:

Objectives	Endpoints
Determine dose response of ALXN1840 15 mg/day and 30 mg/day for copper balance in participants with WD	Assess dose response of ALXN1840 on copper balance focusing on copper balance
Determine the effect of treatment duration on copper balance in participants with WD	Determine the effect of time following initiation of ALXN1840 treatment on copper balance
Assess the effects of ALXN1840 on ceruloplasmin (Cp), ceruloplasmin-bound copper (CpC), LBC profiles in plasma in participants with WD	Cp, CpC, LBC, and Change in Cp at Days 1, 8, 25, 29, 36, and Day 39 compared with pre-dose
Assess dose proportionality at steady state of doses of ALXN1840 15 mg/day and 30 mg/day in participants with WD	Based on PK parameters

Objectives	Endpoints
Assess effects of ALXN1840 on copper:molybdenum ratio in plasma at steady state in participants with WD	Measure plasma copper:molybdenum ratios at steady state compared with pre-dose
Assess the effects of repeat-dose ALXN1840 on copper:molybdenum ratio in urine and feces in participants with WD	Mean daily copper:molybdenum ratio in urine and feces at steady state compared with pre-dose Baseline

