7.2.1.4. Hypothesis Testing and Significance Level

As this study is an exploratory study, no formal hypothesis testing is being conducted. The study results will be summarized using descriptive statistics.

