7.4.3. Pharmacokinetic Parameter Analyses

The following plasma PK parameters, as data permit, will be calculated for total molybdenum and PUF molybdenum (as surrogate measures of ALXN1840 PK) after dosing on Days 1, 25, 29 and 39 using noncompartmental methods with Phoenix® WinNonlin® (Certara USA Inc., Princeton, New Jersey) Version 8.0 or higher or SAS Version 9.4 or higher (SAS Institute Inc., Cary, North Carolina), as applicable. Calculations will be based on the individual actual sampling times relative to the actual ALXN1840 reference dosing times recorded during the study.

- Time delay between the time of dosing and time of appearance of molybdenum concentration (T_{lag}) in plasma
- Maximum observed concentration (C_{max})
- Dose-normalized C_{max} (C_{max_n}); n = dose normalized
- Time to maximum concentration (T_{max})
- Trough (pre-dose) concentration observed at the start of the dosing interval (C_{trough})
- Time of last quantifiable concentration (T_{last})
- Observed concentration at the end of the dosing interval (C_{τ} , where $\tau = 24$ h)
- Area under the plasma concentration versus time curve (AUC) from time 0 to the last quantifiable concentration (AUC_t)
- Dose-normalized AUC_{t_n} (AUC_{t_n}); n = dose normalized
- AUC from time 0 to infinity (AUC_{∞}) (Day 1 only)
- Dose-normalized AUC_{∞} (AUC_{∞_n}); n = dose normalized
- AUC over the dosing interval (AUC_{τ})
- Accumulation ratio (AR) calculated as C_{max} , C_{trough} , and AUC_{τ} after repeat dosing divided by those after initial dosing on Day 1:

For 15 mg/day:

- $C_{max,Day25}/C_{max,Day1}$
- $C_{trough,Day26}/C_{trough,Day2}$
- $AUC_{\tau,Day25}/AUC_{\tau,Day1}$

For 30 mg/day:

- $C_{max,Day39}/C_{max,Day29,adjusted}$
- $C_{trough,Day40}/C_{trough,Day30,adjusted}$
- $AUC_{\tau,Day39}/AUC_{\tau,Day29,adjusted}$

Note: total molybdenum and PUF molybdenum concentration-time profiles on Day 28 after the last 15 mg ALXN1840 dose will be extrapolated to Day 29 (0-24 hr) and subtracted from the

observed Day 29 concentration-time profiles after the first 30 mg ALXN1840 dose for the estimation of the $C_{\max, \text{Day}29, \text{adjusted}}$, $C_{\text{trough}, \text{Day}30, \text{adjusted}}$, and $AUC_{\tau, \text{Day}29, \text{adjusted}}$.

- Apparent terminal phase elimination rate constant (λ_z)
- Terminal elimination half-life ($t_{1/2}$)
- Apparent total body clearance (CL/F) of ALXN1840 from plasma
- Apparent volume of distribution (V_d/F)

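### The dose-proportionality power model lists dose-normalised parameters but is read against a slope of 1; for those parameters proportionality gives a slope of 0

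*SAP*

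**What the plan says.** SAP 5.1.3 has as an exploratory objective: "Assess dose proportionality at steady state of doses of ALXN1840 15 mg/day and 30 mg/day in participants with WD". The matching endpoint, there and in Protocol section 3, refers only to PK parameters and names none.

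SAP 7.4.5 is the only place where the analysis is specified. It starts "If data permit, dose-proportionality for ALXN1840 will be assessed graphically and by using a power model" and continues "The following PK parameters obtained on Days 25 and 39 will be assessed for dose proportionality". Two parameters follow, C_max_n and AUC_t_n, and no others. SAP 7.4.3 explains the suffix ("n = dose normalized") and lists the un-normalised C_max and AUC_t as separate entries.

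The next sentence of 7.4.5 gives the model. The response is the log of the PK parameter for plasma total and PUF molybdenum, and log(dose) "will be included as a fixed effect in the power model". The displayed equation is log(PK Parameter) = mu + beta × log(Dose), and a beta of 1 "indicates perfect dose proportionality". Beta is to be reported with a 90% confidence interval. No acceptance limits are given. An ANOVA is mentioned as a further approach.

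**The concern.** A power-model slope of 1 means proportionality only when the response is exposure itself. If exposure has already been divided by dose, proportionality means that the response does not change with dose, so the slope is 0. Taken as written, 7.4.5 combines the first reference with the second kind of response.

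An analyst who follows the list would obtain a slope near 0 from perfectly proportional data. Read against 1, that looks as if exposure did not rise at all when the dose doubled. Conversely, a slope of 1 from the listed parameters would be reported as perfect proportionality when it actually means a four-fold rise.

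A second, smaller point is that Day 25 (15 mg) and Day 39 (30 mg) profiles come from the same participants, but the displayed equation has no participant term.

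**Working it through.** **Inputs.** Doses are 15 mg/day on Day 25 and 30 mg/day on Day 39 (SAP section 4). The parameters, model and reference value are in SAP 7.4.5, and the suffix is defined in SAP 7.4.3. The sample size is about 10 (SAP 9.1). The documents give no variability figures for these parameters.

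**Step 1: the SAP's reference value.** Let exposure be P = k·D^b. Then log P = log k + b·log D. With two doses, b = ln(P30/P15) / ln 2. Proportional exposure means P30/P15 = 2, so b = ln 2 / ln 2 = 1. The reference of 1 is therefore reproduced for un-normalised parameters.

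**Step 2: the parameters actually listed.** log(P/D) = log k + (b − 1)·log D. The slope is b − 1, which is 0 under proportionality.

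| Exposure ratio 30/15 mg | Slope, un-normalised: ln(ratio)/ln 2 | Slope, dose-normalised |
|---|---|---|
| 1.0 | 0 | −1 |
| 1.6 | 0.68 | −0.32 |
| 2.0 | 1 | 0 |
| 2.5 | 1.32 | 0.32 |
| 4.0 | 2 | 1 |

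The shift is exactly 1 in every row and needs no assumption.

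**Step 3: would another normaliser rescue the text?** SAP 7.2.2 and 7.4.3 give molybdenum-equivalent doses of 3.33 mg and 6.66 mg. Their ratio is 6.66/3.33 = 2, the same as 30/15, so the slope under proportionality is again 0.

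**Step 4: how often would the interval mislead?** This used 20,000 simulated trials with exactly proportional exposure, 10 complete pairs and a paired 90% t-interval. Within-participant CVs of 15%, 25% and 40% are assumed. The interval for the normalised parameters contains 1 in 0.0%, 0.0% and 2.2% of trials, and contains 0 in about 90%. The interval for un-normalised parameters contains 1 in about 90%.

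**Step 5: no participant term (secondary).** Four between/within-participant CV pairs were assumed, with 10 participants, exact proportionality and 100,000 simulated trials each. Half-widths are means for the 90% interval with complete pairs, on 18 degrees of freedom without a participant term and 9 when paired. The last column is the shift in slope, without a participant term, if the 1, 2 or 3 participants with the highest true exposure have no Day 39 profile at 30 mg.

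| CV between/within | Half-width, no term | Half-width, paired | Shift, 1 / 2 / 3 missing |
|---|---|---|---|
| 40/15% | 0.45 | 0.17 | −0.10 / −0.18 / −0.25 |
| 30/20% | 0.39 | 0.23 | −0.07 / −0.13 / −0.19 |
| 50/25% | 0.58 | 0.28 | −0.12 / −0.22 / −0.31 |
| 80/30% | 0.83 | 0.34 | −0.17 / −0.32 / −0.46 |

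With complete pairs the slope is unbiased either way. With a random participant effect (variance components taken as known) the shift over the same cells is −0.01 to −0.07, and it is 0.00 if the missing profiles depend only on the observed Day 25 value. All four half-widths without a participant term are below 1, so even the wider interval around a slope of 0 would on average exclude 1.

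**The case against.** The strongest defence is that the list need not feed the model. It follows a sentence naming two methods, graphs and a power model, with an ANOVA mentioned later, and dose-normalised values suit a plot or an ANOVA. The model sentence describes its response only in general terms, and un-normalised C_max and AUC_t are derived in 7.4.3. On that reading 1 is the right reference and the SAP is merely unclear. The reading is possible, but the text does not state it: there is one list, the model follows directly, and no other parameters are named for it. The Protocol does not help, because its parameter list in 9.4.4 has no dose-normalised entry and it describes no power model. An analyst would have to depart from the list to get the right answer.

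The practical risk is limited, and that part of the defence stands. Under SAP 7.4.3 the parameters are "summarized by analyte, treatment (dose), and day using the following descriptive statistics", so a doubling of C_max and AUC would be visible beside a slope read as no increase. The analysis is conditional on the data permitting it, and SAP 7.2.1.4 says that "no formal hypothesis testing is being conducted".

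On the participant term, the displayed equation is schematic (it shows no error term either), so its silence does not prove that such a term would be left out. The CVs in Step 5 are assumptions. The bias figures are a worst case: Protocol Table 4 lets participants stay on 15 mg for safety concerns, but nothing in the documents links that to high exposure. This point is therefore an improvement to specify, not a demonstrated error.

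**Conclusion.** The inconsistency is real and minor. For the parameters that SAP 7.4.5 lists, the stated reference is wrong by exactly 1; that is algebra and rests on no assumption. Which element is the slip, the list or the reference, cannot be decided from the documents. The misreading occurs only if the model is run on the parameters as listed and then judged against 1. In that case truly proportional exposure would nearly always appear non-proportional, with the interval containing 1 in at most 2.2% of simulated trials under the assumed CVs.

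Only an exploratory objective is affected. The primary and secondary copper-balance results do not depend on it.

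The participant term is secondary. Under the assumed CVs, leaving it out makes the interval about 1.7 to 2.6 times as wide (0.39/0.23 to 0.45/0.17). Bias arises only if participants without a 30 mg profile differ in exposure from the rest.

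**What to change.** Rewrite the power-model paragraph of SAP 7.4.5 so that the parameters and the reference agree, in one of two ways:

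- fit un-normalised C_max and AUC_t, both already derived in 7.4.3, and keep 1 as the reference; or
- keep C_max_n and AUC_t_n and state 0 as the reference.

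If the normalised parameters are wanted for the graphs or the ANOVA, say so separately. In the same edit, include participant as a random effect and add a sentence on how participants without a 30 mg profile on Day 39 are handled.

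The cost is one SAP paragraph. No extra data, samples or visits are needed.
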